9.3.3 Causality of adverse event

The investigator is required to provide a causality assessment for each AE reported to the sponsor. The sponsor will consider the investigator's causality assessment and also provide its own assessment. Assessment of the causal relationship to the study drug will be made according to the following classifications based on Karch FE, et al. [70]:

1. Definite: An event that follows a reasonable temporal sequence from administration of the drug or in which the drug level has been established in body fluids or tissues; that follows a known response pattern to the suspected drug; and that is confirmed by

improvement on stopping the drug (dechallenge), and reappearance of the event on repeated exposure (rechallenge).

- 2. Probable: An event that follows a reasonable temporal sequence from administration of the drug; that follows a known response pattern to the suspected drug; that is confirmed by dechallenge; and that could not be reasonably explained by the known characteristics of the patient's clinical state.
- Possible: An event that follows a reasonable temporal sequence from administration of the drug; that follows a known response pattern to the suspected drug; but that could have been produced by the patient's clinical state or other modes of therapy administered to the patient.
- 4. Doubtful/Unlikely: An event that follows a reasonable temporal sequence from administration of the drug; that does not follow a known response pattern to the suspected drug; but that could not be reasonably explained by the known characteristics of the patient's clinical state.
- 5. Unrelated: Any event that does not meet the criteria above.

The operational tool to decide the AE causal relationship is based on algorithms by Karch-Lasagna and Naranjo (ANNEX 15) [71,72].

When an AE is classified, assessing causal relationship by the Investigator, as "definite", "probable," "possible" or "doubtful/unlikely," the event will be defined as a suspected ADR. A suspected ADR with a causal relationship of "definite" will be defined as an AR. When the causal relationship is labeled "unrelated," then it will be considered that the AE is not imputable to the study treatment, and it is not a suspected ADR.

In addition, when a causal relationship between the study treatment and the AE cannot be ruled out by the Investigator and/or sponsor, it means that the AE cannot be labeled "unrelated".

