9.3.5 Expectedness of adverse event or suspected adverse drug reaction

An AE or suspected ADR is considered "unexpected" if the nature, seriousness, severity or outcome of the reaction(s) is not consistent with the reference information. The expectedness of an AR shall be determined by the sponsor according to the reference document (IB or SPC).

Events not listed for the particular drug under investigation in the IB (or SPC) are considered "unexpected" and those listed are considered "expected." When new AE information is received, it is the sponsor's responsibility to determine whether the event is "unexpected" for IND safety reporting purposes.

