9.3.8.2 Reporting of serious adverse events

Any SAE (see Section 9.3.6) that occurs after signing the ICF and last day of subject's participation in the clinical trial must be expeditiously reported whether or not it is considered attributable to the study drug. Each SAE must be fully recorded in the subject's eCRF.

SAEs will be reported using the designated SAE Report Form. When the Investigator becomes aware of an SAE, she/he must submit it electronically through the electronic data capture (EDC) system within 24 hours. When the EDC system is not available, the SAE is to be reported to the sponsor within 24 hours by emailing or faxing a completed, signed and dated paper SAE Report Form (ANNEX 16, in English). The date of this SAE discovery by the site staff should be documented in the source documents (*i.e.*, medical records).

Each SAE must be followed up until its resolution or stabilization. After the initial report, all relevant follow-up information for SAE including the outcome, must also be supplied to the sponsor in a timely manner (within 3 days from its identification or within 24 hours for relevant new information) via EDC or by means of the SAE Report Form when EDC system is not available. In addition, the sponsor or the CRO may request additional information and/or reports.

All SAE Report Forms must be submitted to Grifols, electronically through the EDC system or with a paper SAE report form when the EDC system is not available, to:

Grifols Global Drug Safety Email: FAX (back-up only): (International)

When required by local law and regulations, SAEs must be reported to the IRB/EC and regulatory authorities.

SAEs will be assessed by the sponsor for expectedness assuming that all subjects have been treated with Flebogamma® 5% DIF. If the causality assessment was considered anything other than unrelated by the Investigator, the event will be considered serious, suspected, potentially related to the study drug and unexpected (SUSAR) and then the treatment allocation will be unblinded to unblinded sponsor staff included in Section 4.3.2 and to the sponsor global pharmacovigilance staff. Anyone involved in site monitoring and analysis or interpretation of data will be kept blinded. The following possibilities resulting from the unblinding will be considered:

- 1. If the study drug administered to the subject is Flebogamma[®] 5% DIF, the case will be reported in accordance to local regulations.

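### The SUSAR trigger in Protocol 9.3.8.2 uses the Investigator's causality alone, although 9.3.3 lets either the Investigator or the sponsor rule out the label unrelated

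*Protocol*

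**What the plan says.** **Causality, Protocol 9.3.3.** The Investigator gives a causality assessment for every adverse event reported to the sponsor. The sponsor is to take account of the Investigator's "causality assessment and also provide its own assessment". A suspected adverse drug reaction is defined from the Investigator's rating ("When an AE is classified, assessing causal relationship by the Investigator, as" definite, probable, possible or doubtful/unlikely). The section closes with a wider rule: when a relationship "cannot be ruled out by the Investigator and/or sponsor, it means that the AE cannot be labeled" unrelated.

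**Expectedness, Protocol 9.3.5.** The sponsor decides expectedness against the reference document: "Events not listed for the particular drug under investigation in the IB (or SPC) are considered" unexpected, and listed events are expected.

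**Seriousness, Protocol 9.3.6.** If either party believes an event is serious, it counts as serious, and the sponsor must evaluate it for expedited reporting.

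**Trigger, Protocol 9.3.8.2.** Every SAE goes to the sponsor within 24 hours, whatever its causality. Then: "SAEs will be assessed by the sponsor for expectedness assuming that all subjects have been treated with" the active product. The next sentence is the trigger: "If the causality assessment was considered anything other than unrelated by the Investigator, the event will be considered serious, suspected". It goes on to call such an event unexpected, names it a SUSAR, and has its allocation disclosed to the sponsor's unblinded staff and its pharmacovigilance staff. After unblinding, a case on active product is reported under local regulations. A case on saline has its expectedness assessed again.

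**The concern.** The protocol requires a sponsor causality assessment and gives it force in 9.3.3, but gives it no role in the one rule that turns causality into SUSAR status. The two sections can therefore give different answers for the same event. The case that matters is an unexpected SAE that the Investigator attributes to something else while the sponsor cannot exclude the product. Under 9.3.3 that event cannot be called unrelated. Under 9.3.8.2 nothing happens to its classification or its blind.

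The trigger sentence also moves from the Investigator's causality straight to the word unexpected, without saying that the sponsor must have found the event unexpected. Someone applying that sentence alone would not see that expectedness is part of the test.

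At stake is whether SUSAR classification is applied consistently. No estimate, test or sample size in the plan depends on it.

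**Working it through.** No arithmetic applies. The check sets the sections side by side.

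**1. Causality.** Take an SAE that the sponsor has assessed as unexpected, and go through the four pairings of Investigator and sponsor opinion. The third column follows the closing rule of 9.3.3; the fourth follows the trigger in 9.3.8.2.

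| Investigator | Sponsor | May it be labelled unrelated (9.3.3)? | Does the trigger fire (9.3.8.2)? | Consistent? |
|---|---|---|---|---|
| Not unrelated | Not unrelated | No | Yes | Yes |
| Not unrelated | Unrelated | No | Yes | Yes |
| Unrelated | Cannot rule out | No | No | **No** |
| Unrelated | Unrelated | Yes | No | Yes |

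The sections disagree in one of four pairings. This counts logical cells. It is not a share of events.

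**2. Is 9.3.3 uniform?** No. It defines a suspected adverse drug reaction by the Investigator's rating, then closes with the rule that brings in the sponsor. The trigger matches the definition but not the closing rule. Changing 9.3.8.2 alone would leave that difference inside 9.3.3.

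**3. What still happens in the third pairing?** The SAE is sent to the sponsor within 24 hours, because that duty does not depend on causality. The sponsor evaluates it for expedited reporting under 9.3.6. Neither provision says whose causality opinion governs that evaluation; the only rule that names an assessor for SUSAR status names the Investigator. What is missing under the written trigger is SUSAR classification and the unblinding that follows.

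**4. Expectedness.** The sentence before the trigger has the sponsor assess SAEs for expectedness on the assumption of active treatment. In the saline branch the event is assessed a second time and may remain unexpected, which presupposes that the sponsor had already judged it unexpected. The active branch needs no second look, because the first already assumed active product. The sequence is coherent. What is absent is a clause in the trigger sentence that makes the sponsor's result a condition.

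**The case against.** The strongest reply is that the procedure works when read whole. Every SAE reaches the sponsor promptly. Section 9.3.6 requires an evaluation for expedited reporting. Section 9.3.5 makes the sponsor responsible for expectedness. Section 9.3.3 already forbids the label unrelated when the sponsor has doubts. The sponsor's medical monitor also reviews reported events for thromboembolism and haemolysis (9.3.7.1, 9.3.7.2). On this view the trigger is loosely drafted and no event is mishandled.

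Much of that stands, and it limits the consequence to classification and unblinding. It does not close the gap. Section 9.3.3 bars a label but provides no step by which the sponsor's doubt replaces the Investigator's rating, and the trigger reads the Investigator's rating.

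A reader might infer three stronger points that the documents do not support:

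- *That the expectedness test is skipped.* It is in the sentence directly before the trigger, and the saline branch presupposes its result.
- *That every expected SAE rated as related is unblinded.* This follows only if the trigger sentence is read apart from its neighbours and from 9.3.5. Which events are expected depends on the reference document, and the protocol's general risk text does not settle that.
- *That the blind of the efficacy analysis is at risk.* Section 9.3.8.2 confines unblinding to unblinded sponsor staff and pharmacovigilance and keeps those who monitor sites or analyse data blinded. Section 4.3.2 already excepts the sponsor's drug safety staff.

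Nor does SAP 11.1 need to change. It defines suspected adverse drug reactions by causality category without naming an assessor, and is not shown to contradict the Investigator-based definition in 9.3.3.

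**Conclusion.** The concern holds as an internal inconsistency. Section 9.3.3 gives the sponsor's doubt the power to prevent the label unrelated; the trigger in 9.3.8.2 ignores it. An unexpected SAE that only the sponsor suspects is not classified or unblinded as a SUSAR under the written rule, although it is reported to the sponsor and evaluated under 9.3.6. The missing expectedness condition is a secondary drafting defect.

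This rests on two readings: that the closing rule of 9.3.3 means either party is enough, and that the trigger means what it says in naming only the Investigator. Frequency cannot be stated without SAE rates and the rate of disagreement between the two assessors. The point is worth correcting because it concerns patient safety and the correction is cheap.

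**What to change.** Reconcile 9.3.8.2 with 9.3.3 and 9.3.5 by rewording the trigger along these lines:

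> An SAE is handled as a SUSAR, and its allocation is unblinded to the staff named here, when its causality is other than unrelated in the assessment of the Investigator or of the sponsor (9.3.3) and the sponsor has assessed it as unexpected (9.3.5).

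In 9.3.3, state how the Investigator-based definition of a suspected adverse drug reaction relates to the closing rule.

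The cost is one sentence in 9.3.8.2 and a clarification in 9.3.3. A few more events may be handled as SUSARs on the sponsor's assessment. No analysis changes.

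SAP section 2 records that the trial was ended early as a business decision, so an amendment may have little prospective effect. In that case, checking whether any SAE had the discordant pairing, and noting how it was handled, would serve the same purpose.

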9.3.4 Intensity of adverse event or suspected adverse drug reaction

AEs and suspected ADRs will be classified depending on their intensity according to the following definitions:

- 1. Mild: an AE which is well tolerated by the subject, causing minimum degree of malaise and without affecting normal activities.
- 2. Moderate: an AE that interferes with the subject's normal activities.
- 3. Severe: an AE that prevents the subject from performing their normal activities.

AE and suspected ADR intensity gradation must be distinguished from AE and suspected ADR seriousness gradation, which is defined according to event consequence. For example, headache can be mild, moderate or severe but unusually is serious in all these cases.

The Investigator will be responsible for assessing the AE and suspected ADR intensity during the clinical trial, taking into account currently criteria included in this section.

9.3.5 Expectedness of adverse event or suspected adverse drug reaction

An AE or suspected ADR is considered "unexpected" if the nature, seriousness, severity or outcome of the reaction(s) is not consistent with the reference information. The expectedness of an AR shall be determined by the sponsor according to the reference document (IB or SPC).

Events not listed for the particular drug under investigation in the IB (or SPC) are considered "unexpected" and those listed are considered "expected." When new AE information is received, it is the sponsor's responsibility to determine whether the event is "unexpected" for IND safety reporting purposes.

9.3.6 Seriousness of adverse event or adverse reaction; serious adverse event

An AE or suspected ADR is considered "serious" if, in the view of either the investigator or sponsor, it results in any of the following outcomes:

- 1. Death.
- 2. Life-threatening AE (life-threatening in the definition of "serious" refers to an event in which the subject was at risk of death at the time of the event; it does not refer to an event which hypothetically might have caused death if it were more severe).
- 3. In-patient hospitalization or prolongation of existing hospitalization.

Note: hospitalization is to be considered only for hospital stays for \geq 24 hours.

The following hospitalizations should not be reported as SAEs:

- Hospitalization or prolongation of hospitalization needed for procedures required by the clinical trial protocol.
- Hospitalization or prolongation of hospitalization as part of a routine procedure followed by the center.
- Hospitalization for a survey visit, annual physicals, or social reasons.
- Elective (preplanned) hospitalizations for a pre-existing condition that had not worsened from Baseline (e.g., elective or scheduled surgery arranged prior to start of the study).

- Admissions not associated with an AE (e.g., social hospitalization for purposes of respite care).
- A persistent or significant incapacity or substantial disruption of the ability to conduct normal life functions.
- 5. A congenital anomaly/ birth defect.
- 6. An important medical event (important medical event in the definition of "serious" refers to those events which may not be immediately life-threatening, or result in death, or hospitalization, but from medical and scientific judgment may jeopardize the subject or/and may require medical or surgical intervention to prevent one of the other outcomes listed above.

This definition permits either the sponsor or the Investigator to decide whether an event is "serious". If either the sponsor or the Investigators believes that the event is serious, the event must be considered "serious" and evaluated by the sponsor for expedited reporting.

A distinction should be drawn between serious and severe AEs. The term "severe" is used to describe the intensity (severity) of a specific event; the event itself, however, may be of relative minor medical significance (such as severe headache). This is not the same as "serious", which is defined on subject/event outcome or action criteria usually associated with events that pose a threat to a subject's life or functioning. Seriousness (not severity) is a medical term while severity is a subjective term.

According to the medical criteria, an AE or a suspected ADR can be classified as serious, although it does not fulfill the conditions fixed in this section, if it is considered important from a medical point of view.

9.3.7 Adverse events of special interest

9.3.7.1 Thromboembolic events

Subjects will be monitored for signs and symptoms of arterial and venous thromboembolic (TE) events. In addition, the Grifols Medical Monitor (Clinical Assessment Monitor) will routinely review reported AEs for possible TE events. Arterial and venous TE events will be identified according to definitions in the International Classification of Diseases, Ninth Revision, Clinical Modification (ICD-9-CM). Such events include, but are not limited to, DVT, PE, acute myocardial infarction, cerebral infarction, acute ischemic heart disease, embolism or thrombosis of arteries of lower extremities, sagittal sinus thrombosis, and portal vein thrombosis and injury of mesenteric artery. All TE events will be recorded as AEs and reported accordingly.

9.3.7.2 Hemolysis

Subjects will be monitored for signs and symptoms of hemolysis. In addition, the Grifols Medical Monitor (Clinical Assessment Monitor) will routinely review reported AEs for possible hemolysis. Hemolysis will be recorded as AEs and reported accordingly.

9.3.8 Procedures for eliciting reports of and for recording and reporting adverse events and adverse reactions

The occurrence and follow-up details of all AEs experienced by any of the subjects during the clinical trial, from signature of the *Clinical Trial Written Informed Consent Form* to the last follow-up visit, will be recorded on the AE eCRF entry and in the subject's hospital record. If no AE has occurred during the study period, this should also be indicated in the eCRF.

At each visit, AEs will be elicited by asking the individual a non-leading question such as "Do you feel different in way since the last visit?" Moreover, AEs will also be collected through directly observed events or spontaneously volunteered by the subject. Clearly related signs, symptoms and abnormal diagnostic procedures preferably should be grouped together and recorded as a single diagnosis or syndrome wherever possible. It is responsibility of the Investigator to ensure that AEs are appropriately recorded.

The following variables must be recorded on the AE eCRF entry:

- 1. the verbatim term (a diagnosis is preferred)
- 2. date/time of onset
- 3. date/time of resolution
- 4. intensity (mild, moderate, severe)
- 5. causality (unrelated, doubtful/unlikely, possible, probable, definite)*
- 6. seriousness (yes, no)
- 7. action taken (with regard to study drug)
- 8. other action (to treat the event)
- 9. outcome and sequel (follow-up on AE)

*Causality assessment will be only made when the AE occurs after the subject has received one or another study treatment. AE occurring before subject's exposure to study treatments will be always labeled as "unrelated".

For AEs that occur during infusions, the infusion rate in effect at the time of onset of the AE, the time of onset of the AE and the time of AE change materially in intensity and/or resolve will be captured the eCRF entry.

In addition to the Investigator's own description of the AEs, each AE will be encoded by the sponsor (CRO) according to the Medical Dictionary for Regulatory Activities (MedDRA®).

The Development Safety Update Report (DSUR) for the investigational product Flebogamma® DIF is prepared by the sponsor of the clinical trial in compliance with the ICH Guideline "E2F Development Safety Update Report". The DSUR is annually submitted by the sponsor to the Competent Authorities on Medicines in the countries where the sponsor has been performing clinical trials with the investigational product Flebogamma® DIF.

A DSUR Executive Summary, supplemented with line listings of serious adverse reactions (SARs), is also annually submitted by the sponsor to ethics committees (ECs)/institutional

review boards (IRBs), where national or regional laws or regulations require submission of an annual safety report on an investigational product.

9.3.8.1 Reporting pregnancy

While pregnancy itself is not a true "AE," pregnancy occurring in a clinical study must be followed to collect information regarding the experiences of gestation and pregnancy with investigational product exposure. The Investigator must report any pregnancy that occurs in a female study subject or partner of a male study subject subsequent to informed consent until 28 days after the last dose of investigational product.

A pregnancy not verified before randomization but occurring during the course of the study will be not considered an AE, unless a relation to the study drug is suspected. In any case, a *Pregnancy Report Form must be completed* and sent as soon as possible to the sponsor, and the study treatment must be discontinued. A copy of the form should be filled at the study site for follow-up until the end of the pregnancy.

Any pregnancy occurring in a female study subject or partner of a male study subject must be followed by the Investigator until delivery or to the end of pregnancy. Any anomalies, complications, abnormal outcomes, or birth defect observed in the child must be reported as an SAE within 24 hours of the Investigator's or study personnel's first knowledge. Please use the email address or fax numbers (back up only) in Section 9.3.8.2 for reporting pregnancy.

9.3.8.2 Reporting of serious adverse events

Any SAE (see Section 9.3.6) that occurs after signing the ICF and last day of subject's participation in the clinical trial must be expeditiously reported whether or not it is considered attributable to the study drug. Each SAE must be fully recorded in the subject's eCRF.

SAEs will be reported using the designated SAE Report Form. When the Investigator becomes aware of an SAE, she/he must submit it electronically through the electronic data capture (EDC) system within 24 hours. When the EDC system is not available, the SAE is to be reported to the sponsor within 24 hours by emailing or faxing a completed, signed and dated paper SAE Report Form (ANNEX 16, in English). The date of this SAE discovery by the site staff should be documented in the source documents (*i.e.*, medical records).

Each SAE must be followed up until its resolution or stabilization. After the initial report, all relevant follow-up information for SAE including the outcome, must also be supplied to the sponsor in a timely manner (within 3 days from its identification or within 24 hours for relevant new information) via EDC or by means of the SAE Report Form when EDC system is not available. In addition, the sponsor or the CRO may request additional information and/or reports.

All SAE Report Forms must be submitted to Grifols, electronically through the EDC system or with a paper SAE report form when the EDC system is not available, to:

Grifols Global Drug Safety Email: FAX (back-up only): (International)

When required by local law and regulations, SAEs must be reported to the IRB/EC and regulatory authorities.

SAEs will be assessed by the sponsor for expectedness assuming that all subjects have been treated with Flebogamma® 5% DIF. If the causality assessment was considered anything other than unrelated by the Investigator, the event will be considered serious, suspected, potentially related to the study drug and unexpected (SUSAR) and then the treatment allocation will be unblinded to unblinded sponsor staff included in Section 4.3.2 and to the sponsor global pharmacovigilance staff. Anyone involved in site monitoring and analysis or interpretation of data will be kept blinded. The following possibilities resulting from the unblinding will be considered:

- 1. If the study drug administered to the subject is Flebogamma[®] 5% DIF, the case will be reported in accordance to local regulations.
- 2. If the study drug administered to the subject is Normal Saline Solution, the suspected ADR will be reassessed for expectedness according to the reference safety information and:
 - a. If the suspected ADR is still considered unexpected, it will be reported in accordance with applicable requirements and guidelines.
 - b. If the suspected ADR is considered expected, it will not be reportable on an expedited basis, unless specifically requested by local regulations.

